## Abstract/Summary of the research

Professional musicians are exposed to chronic high volume of continuous and repeated physical movements, sometimes in challenging and ergonomically unfavourable anatomical body positions, in order to acquire and improve technical playing skills. As a consequence, musicians are vulnerable to developing adverse playing-related musculoskeletal disorders (PRMDs) that may affect the manner in which and the extent to which music can be practised and performed.

In order to find out effective solutions for PRMDs and to develop future preventive measures, it is fundamental to firstly identify the main risk factors that play a significant role in the development of adverse musculoskeletal (MSK) conditions and symptoms.

The aim of the study will be to identify those factors associated with increased risk of PRMDs among music students. A further goal is to characterise and describe the clinical features of PRMDs, as well as determine the evolving course of PRMD's in music students during their professional training.

All pre-college and university-level students from several European music academies will receive an invitation to complete a web-based questionnaire survey at each of three occasions (baseline; 6-months follow-up; 12-months follow-up).

The web-based survey will include questions about any pain, PRMD and/or MSK problem they may have due to their musical practice, and different outcome measures (i.e. lifestyle and physical activity, practice habits, behaviour toward prevention and health history, level of stress, perfectionism, fatigue and disability).

To the best of our knowledge, no other longitudinal studies on risk factors for PRMDs have been conducted so far. Therefore, the study can be considered as an opportunity to fill the gaps of current research on PRMDs and generate new knowledge in educational and employment musical contexts.

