# Methodology

#### Study Design

This prospective longitudinal cohort study will be conducted through the following three phases (Figure 1):

- (1) A baseline cross-sectional survey to characterise the study population and subgroups, and form the basis for the evaluation of associated factors and relationships with the development of PRMDs;
- (2) A 6-months follow-up survey, and
- (3) A 12-months follow-up survey.

[figure not shown]

Figure 1 Research planning chart including main features of the cohort study

The study protocol has been approved by the Research Ethics Panel of the Queen Margaret University, Edinburgh (REP 0177).

After the first baseline data collection (Phase 1), the cohort of students will be broken down into:

- Cohort 1: music students (both pre-college and university-level) who are free of pain, PRMDs and/or MSK problems at baseline data collection
- Cohort 2: music students (both pre-college and university-level) who aren't free of pain, PRMDs and/or MSK problems at baseline data collection

Afterwards, the two cohorts will be followed and invited for reassessment at 6 months (Phase 2) and 12 months (Phase 3).

The 6-months and 12-months follow-ups for the Cohort 1 will be essential to monitor and record the development of new incidents of invasive pain, PRMDs and/or MSK problems within a period of a year and to enable characterisation of the nature and time course of developing pain, PRMDs and/or MSK problems.

The analysis of the results will attempt to answer primary research question and secondary research question 3 and 4, addressing the lack of any similar type of data in the current literature.

Similarly, the follow-ups for the Cohort 2 will be important in order to characterise the impact and time course of changes in any pain, PRMD and/or MSK problem within a 12-month period.

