# The web-based survey

The web-based survey will include different outcome measures, which have been selected according to the relevant findings of previous cross-sectional studies and systematic reviews among the performing arts literature (Figure 2).

Each outcome measure correspond to a suspected factor that may be associated with the development of PRMDs.

The survey will start with questions about personal background and lifestyle (i.e. age, gender, self-reported weight and height, nationality, smoking status and sleeping habits), as well as practice habits (i.e. number of

hours of practice and years of experience) health history (i.e. major past injuries/accident/disorders and current medication) and health status (Self-Related Health - SRH).

Afterwards, in order to divide the cohorts, the presence of pain and/or MSK problems will be assessed through the following question: "When did you last experience a bout of significant pain and/or musculoskeletal problem?" with the following list of possible answers:

- 1. I currently have pain and/or a musculoskeletal problem (up to one month)
- 2. 2-3 months ago
- 3. 4-6 months ago
- 4. Up to 12 months ago
- 5. More than 12 months ago
- 6. I have never had any pain and/or musculoskeletal problem

[figure not shown]

Figure 2 Procedure of the web-based survey

According to the answer to this question, students will be addressed to different web pages throughout the survey (Figure 2):

- Respondents with a current pain and/or MSK problem (up to one month) will be asked questions to describe their current pain, to report their disability with Pain Disability Index (PDI), the Performing Arts

Section of Quick Disabilities of the Arm, Shoulder and Hand Outcome Measure (PAS –Quick DASH) and their pain self-efficacy with 2-item short form of the Pain Self-efficacy Questionnaire (PSEQ-2), as well as the Nordic Musculoskeletal Questionnaire (NMQ) for the assessment of musculoskeletal pain in the last 12 months

- Respondents without a current pain and/or MSK problem but a positive history of pain and/or MSK problem in the last 12 months (2-3 months ago, 4-6 months ago or up to 12 months ago) will be asked to answer the NMQ and questions on pain management to investigate how their pain and/or MSK problem has been treated
- Respondents without pain or with pain and/or MSK more than 12 months ago will be directly addressed to the next section

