#### Data analysis

Descriptive statistics will be used to investigate all the outcomes after the baseline data collection.

Furthermore, comparisons of gender, study, prevalence rate and hours of practice between pre-college and university-level students of music will be performed.

Baseline variables will be categorized to permit the calculation of risk ratios and the 95% confidence intervals (CI) for the development of PRMDs. Tests for trend of relative risk across categories will be carried out using the chi-square test. In order to check for confounders, logistic regression will be performed, adjusting for age, gender and different musical instrument.

Sample size estimation is reported in Figure 1.

Both the follow-ups will permit longitudinal change in outcome scores to be generated and compared (longitudinal comparisons) for strength and progression of association, alongside those from absolute outcome scores at several cross-sectional analyses.

For the evaluation of the association between the variables (gender, instrument group, age, years of playing, hours of practice, and questionnaires' scores) and pain, PRMD and/or MSK problem incidence, univariate analysis will be performed. Afterwards, all predictor variables that are significantly associated with the

occurrence of PRMDs will be included in a multivariate regression model to estimate the mutually adjusted effect of predictors on PRMDs.

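### PDI, PAS-QuickDASH and PSEQ-2 are collected only from students in current pain, so change from baseline on these three scales leaves out Cohort 2 students who have recovered by follow-up.

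*Protocol*

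**What the plan says.** In the Protocol, under The web-based survey, a six-option question on the last bout of pain decides which pages follow: "According to the answer to this question, students will be addressed to different web pages throughout the survey". There are three routes.

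- Current problem (option 1): "Respondents with a current pain and/or MSK problem (up to one month) will be asked questions to describe their current pain", followed by PDI, PAS-QuickDASH, PSEQ-2 and the NMQ.
- Problem in the last 12 months but not now (options 2 to 4): these students "will be asked to answer the NMQ and questions on pain management to investigate how their pain and/or MSK problem has been treated".
- Everyone else: "Respondents without pain or with pain and/or MSK more than 12 months ago will be directly addressed to the next section".

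The next section, given to all, holds IPAQ-SF, K-10, HFMPS-SF and CFQ-11. The SRH item comes before the routing question.

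The Abstract says that students "complete a web-based questionnaire survey at each of three occasions (baseline; 6-months follow-up; 12-months follow-up"), and it lists disability among the outcome measures. Study Design defines Cohort 2 as students "who aren't free of pain, PRMDs and/or MSK problems at baseline data collection" and follows them to "characterise the impact and time course of changes in any pain, PRMD and/or MSK problem within a 12-month period". Data analysis adds: "Both the follow-ups will permit longitudinal change in outcome scores to be generated and compared". It makes no exception for scales that only some respondents receive.

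**The concern.** PDI and PAS-QuickDASH are the only instruments that the protocol presents as disability measures, so much of the impact objective for Cohort 2 rests on them. Whether a follow-up score exists on them depends on the outcome itself: a student who still hurts is asked, and a student who has recovered is not. That is missingness determined by recovery, not by chance. An average change computed from the available pairs then describes a group selected for a poor course. It could easily be read as the experience of all students who had pain at baseline.

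The 6-month and 12-month averages would also come from different students, because the selection is applied afresh at each survey.

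**Working it through.** **Step 1. Trace the routing.** Apply the stated rule at baseline and at one follow-up.

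| Baseline | Follow-up | Scores on the three scales | Change from baseline |
|---|---|---|---|
| Current pain | Current pain | Both | Exists |
| Current pain | No current pain | Baseline only | Does not exist |
| No current pain | Current pain | Follow-up only | Does not exist |
| No current pain | No current pain | Neither | Does not exist |

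Only the first row yields a change score. It includes students who recovered and relapsed: someone pain-free at 6 months and in pain at 12 months has a 12-month change but no 6-month change. The second row is the recovered part of Cohort 2. The third row covers Cohort 1 students who develop pain, who have no baseline value for comparison.

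**Step 2. Find the direction of the error.** The plan gives no figure to reproduce. Take the students scored at baseline and assume that all respond at follow-up. Let r be the share without current pain at follow-up, dR the mean change they would have shown, and dS the mean change in those in pain at both surveys. A negative change is an improvement.

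- Mean change in the whole group = r × dR + (1 − r) × dS
- Mean change available under the routing = dS
- Available minus whole group = dS − [r × dR + (1 − r) × dS] = r × (dS − dR)

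Improvement is understated whenever recovered students improve more than those still or again in pain. That is the usual case on a disability scale. The error grows in proportion to r.

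**Step 3. Illustrate, with every input assumed.** Suppose recovered students start at 15 to 20 points and end at 0 to 2, so dR lies between 2 − 15 = −13 and 0 − 20 = −20. Suppose dS lies between 0 and −2. Then dS − dR runs from −2 + 13 = 11 to 0 + 20 = 20.

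| r | Share with a change score | Available mean change | Whole-group mean change | Understatement, r × (dS − dR) |
|---|---|---|---|---|
| 20% | 80% | 0 to −2 | −2.6 to −5.6 | 2.2 to 4.0 |
| 40% | 60% | 0 to −2 | −5.2 to −9.2 | 4.4 to 8.0 |
| 60% | 40% | 0 to −2 | −7.8 to −12.8 | 6.6 to 12.0 |

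For example, at r = 20% the ends of the whole-group range are 0.2 × (−13) + 0.8 × 0 = −2.6 and 0.2 × (−20) + 0.8 × (−2) = −5.6. The available mean stays at 0 to −2 whatever r is, so it carries no information on how many recovered. The table shows the mechanism and does not estimate its size in this study.

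**The case against.** **The follow-up routing is inferred.** The routing question is introduced as the means of dividing the cohorts, which is a baseline task, and Figures 1 and 2 are not shown. This stands as a limit on certainty. But the text describes one survey and three occasions, and nowhere says that recovered students answer these scales.

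**Recovery is not hidden.** This stands. If the routing repeats, so does the timing question, which everyone answers, and students with pain in the last 12 months also complete the NMQ. A reader might infer that the course of PRMDs will look more persistent than it is. The documents do not support that, because persistence can be read from the timing question. What is lost is the disability and self-efficacy score.

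**Most change scores are intact.** A reader might infer that all planned change scores describe only students who stayed in pain. They do not: IPAQ-SF, K-10, HFMPS-SF, CFQ-11 and SRH reach every respondent. Even on the three affected scales, the group is those in current pain at both surveys.

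**The analysis is not specified to that level.** Data analysis names none of these three scales and sets out no comparison of their change between training levels or instruments. It would go too far to say that a planned comparison is distorted. One would be, if it were made and recovery differed between the groups. A separate analysis plan could settle how recovered students are handled, but it cannot recover answers that were never collected.

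**Recovered students could be set to no disability at analysis.** This is possible from the timing question, but it would assign that value to every student without current pain, including any whose playing or daily activity is still limited. Asking them is better.

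**Conclusion.** The point holds for PDI, PAS-QuickDASH and PSEQ-2 only. Followed as written, the routing yields change from baseline on them solely for students in current pain at both surveys, and the resulting mean change in disability will usually understate improvement in Cohort 2. This rests on two assumptions: that the single described routing applies at every survey, and that recovered students improve more than the others.

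No percentage or number of points can be attached to the understatement from the documents. Any such figure rests wholly on assumed recovery rates and scores. The matter is secondary to the risk-factor question, but it should be corrected before the follow-up surveys because the loss is permanent.

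**What to change.** State the follow-up routing in the protocol and change it as follows.

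- At 6 and 12 months, give PDI and PAS-QuickDASH to every student who completed them at baseline, whatever the current answer to the timing question. Tying the rule to baseline completion, not to Cohort 2 membership, avoids asking for change from students who have no baseline score. That could arise because the cohort definition does not say whether options 2 to 4 count as free of pain.
- Where items cannot be answered because there is no pain, score them as no disability, and report the proportion recovered beside the mean change.
- Report PSEQ-2 change as conditional on current pain at both surveys. Do not impute a value for recovered students, since the protocol defines no score on pain self-efficacy for a pain-free student.

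The cost is one branching rule in the online survey, a short addition to the protocol, and a few extra minutes for recovered students.

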#### Research questions and hypotheses

Primary research question:

What are the main factors associated with increased risk of PRMDs in music students undertaking professional training?

Secondary research questions/objectives:

- 1. What is the prevalence of musculoskeletal disorders among university-level students in comparison with pre-college students?
- 2. Monitor and characterise the impact of the transition between pre-college and university-level music training on the development of PRMDs.
- 3. (Are there any differences in the severity and symptoms associated with PRMDs among music student groups at different levels of music training?)
- 4. Monitor and characterise the time course of PRMD development

- 5. (Are there significant differences in PRMD incidence between university-level students and pre-college students?
- 6. During training, do music students develop any type of musculoskeletal disorder that doesn't affect their ability to play at the level to which they are accustomed to?
- 7. Characterise health related quality of life and outcomes in music students at different stages of professional training.

Considering the aims and the research questions of the programme, the following hypotheses are formulated:

H1: The development of PRMDs is associated with a multitude of risk factors (i.e. age, gender, number of hours of practice, previous history of injury, poor physical status, psychological stress, perfectionism, fatigue) among music students.

H2: There is a higher prevalence of PRMDs among university-level students in comparison with precollege students.

H3: There is a higher prevalence of PRMDs among university-level students in the early stages of their training (transition between university-level and pre-college).

H4: University-level students develop more PRMDs over the years of their training than pre-college students.

H5: During their training, music students of both levels develop MSK disorders that affect their ability to play at the level they are accustomed to.

H6: Health and quality of life among music students is progressively poorer over the years of training (from the last two years of pre-college to the last years of Master-level)

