#### **Participants**

All pre-college and university-level students from all European music academies will receive an invitation to complete a web-based questionnaire survey.

Pre-college will include third-year and fourth-year students (age: 18 and 19 years old). University-level will include students enrolled in the first, second and third year of the Bachelor degree course (age: between 19, 20 and 22, 23 years old), as well as students enrolled in the first, second and third year of Master degree course (age: between 22, 23 and 35 years old).

Inclusion criteria will be music students, men and women, aged 18 to 35 years old with a classical instrument as main subject (composers and conductors will be excluded).

Exclusion criteria will be composers and conductors, positive history for neurological, rheumatic, psychological disorders or emotional distress, as well as surgery of the upper limbs and/or the spine in the last year.

Blind recruitment will be used. The researcher will contact the student registries of the centres with an invitation e-mail that will be addressed to their student body.

The e-mail will contain information on the study, an information sheet and the link for the online survey. Once opened the link, students will be directed to the electronic consent form, which must be completed and signed before initiating any study procedure. Afterwards, once they have completed and signed the consent, they will be directed to the online-survey.

Questionnaire data and personal information provided through participant informed consents will be stored separately.

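### No described survey item dates a problem's onset or entry to the current training level, so 12-month windows that cross university entry blur the transition and level comparisons

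*Protocol*

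**What the plan says.** Groups are formed by year of enrolment. Under Participants, "Pre-college will include third-year and fourth-year students (age: 18 and 19 years old"); the university group is Bachelor years 1 to 3 and Master years 1 to 3. The wording of H6, "from the last two years of pre-college to the last years of Master-level", shows that the third and fourth years are the final pre-college years.

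Several aims depend on level. Secondary objective 2 concerns the transition to university, question 5 asks about PRMD incidence by level, and H2 compares prevalence. The remaining two hypotheses read "H3: There is a higher prevalence of PRMDs among university-level students in the early stages of their training" and "H4: University-level students develop more PRMDs over the years of their training than pre-college students". The Study procedure section assigns secondary questions 1, 2 and 5 to Phase 1, the baseline survey.

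The survey has two time frames. The item that divides the cohorts asks "When did you last experience a bout of significant pain and/or musculoskeletal problem", with banded answers starting at "I currently have pain and/or a musculoskeletal problem (up to one month"). Anyone with a problem in the past year also completes the "Nordic Musculoskeletal Questionnaire (NMQ) for the assessment of musculoskeletal pain in the last 12 months". Looking forward, Study Design says that the follow-ups of Cohort 1 record "new incidents of invasive pain, PRMDs and/or MSK problems within a period of a year".

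Data analysis plans a comparison of prevalence between levels. It names no window and does not say how a student whose level changes within a window is handled.

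**The concern.** Level is treated as a fixed label, yet for the students at the transition it changes inside the measurement window. A first-year Bachelor student who reports pain over the past 12 months is partly reporting pre-college pain. A fourth-year pre-college student followed for 12 months may spend part of that time at university.

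If university risk is higher, as the hypotheses suppose, either kind of mixing pulls the levels together. A null result for H3 could then reflect the window rather than the transition. Assigning question 5 to Phase 1 sharpens the problem: a single survey can give incidence only by looking back, so there the look-back carries the comparison.

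This is more than analysis detail. What the survey does not ask at baseline cannot be fully recovered by a later analysis plan.

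**Working it through.** The plan gives no figure to reproduce. The sample size is in Figure 1, which is not shown, and does not bear on this point. The check is the overlap of the windows with university entry.

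**Inputs from the protocol**
- Look-back: 12 months (The web-based survey).
- Follow-up: 12 months, with surveys at 6 and 12 months (Study Design).
- Two pre-college year groups and six university year groups (Participants).

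**Assumptions**
- *s* is the number of months from the start of the academic year to baseline. The time-plan shading is lost. The only hints are that T1 begins in September and that a file name in Data management carries the date 1 October 2018. These suggest *s* = 1 but do not establish it.
- Fourth-years enter university at the next academic year.
- Problems arise evenly over time, with 12-month figures of 20% in pre-college and 30% in every university year, a true difference of 10 points.
- Half of the pre-college group is in fourth year, and the six university years are of equal size.

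**Formulas**
- Share of a first-year's look-back that is pre-university: (12 − s)/12.
- Share of a fourth-year's follow-up that is at university: s/12.
- H3, first-years against pre-college on a 12-month look-back: 10 × s/12.
- H2, all university against pre-college on the same look-back: 10 × [1 − (1/6)(12 − s)/12].
- H4, if read from 12-month follow-up by baseline level: 10 × [1 − 0.5 × s/12].

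| s (months) | Look-back before entry | Follow-up after entry | H3 (points) | H2 (points) | H4 (points) |
|---|---|---|---|---|---|
| 1 | 92% | 8% | 0.8 | 8.5 | 9.6 |
| 3 | 75% | 25% | 2.5 | 8.75 | 8.75 |
| 6 | 50% | 50% | 5.0 | 9.2 | 7.5 |
| 9 | 25% | 75% | 7.5 | 9.6 | 6.25 |

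The two shares always sum to 100%, so an early survey makes the look-back error large and the follow-up error small, and a late survey does the reverse.

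**Check with constant hazards.** Take assumed 12-month risks of 0.30 (pre-college) and 0.45 (first-year university), a true difference of 0.15. The annual hazards are −ln(0.70) = 0.357 and −ln(0.55) = 0.598. The observed first-year risk is 1 − exp{−[0.357(12 − s) + 0.598s]/12}. The observed H3 difference is 0.014 at s = 1, 0.041 at s = 3, 0.080 at s = 6 and 0.116 at s = 9. The H4 difference, with half of pre-college in fourth year, is 0.143, 0.130, 0.110 and 0.092. The pattern is the same.

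**What the 6-month survey does.** With an autumn baseline (s = 1 to 3), the first six months of follow-up contain no university time for fourth-years. The second six months contain 1/6 = 17% to 3/6 = 50%.

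**What the survey can recover.** The banded item dates only the last bout. For a first-year at s = 1, an answer of two months or longer ago places that bout before entry, provided the entry month is known. A current problem may have begun on either side of entry, and earlier bouts are hidden behind the last one.

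**The case against.** The strongest reply is that the protocol never states the rule that would do the harm. A reader might infer that problems are counted against the level held at the survey date and that prevalence is the 12-month NMQ figure. The text supports neither: Data analysis speaks only of a prevalence rate, the NMQ is described as measuring musculoskeletal pain rather than PRMDs, and the survey already collects current problems. Choosing the window is commonly left to the analysis plan. This stands, and the point does not rest on either inference.

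A reader might also infer that the same students carry both errors. They do not: at baseline the look-back error falls on first-year Bachelor students and the follow-up error on fourth-year pre-college students.

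Nor does H4 rest mainly on students who cross. Third-years remain in pre-college and existing university students remain at university. H4 also speaks of the years of training rather than a 12-month window. Study Design links the Cohort 1 follow-ups to the primary question and secondary questions 3 and 4, so an H4 analysis from follow-up is itself an assumption.

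Finally, the described items may not be the whole questionnaire. Figure 2 is not shown, and respondents with a current problem get unlisted questions about their pain, which could include its duration. That would cover onset of current problems only.

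What remains is that the windows necessarily cross entry for these students, that Phase 1 is asked to supply incidence and the transition, and that the text describes no item for onset or entry to the current level.

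**Conclusion.** The concern holds as a gap in data collection for the transition and level comparisons. It does not show that the protocol has adopted a wrong counting rule.

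For the transition contrast the effect could be large. With baseline 1 to 6 months after entry, 92% to 50% of a first-year's look-back is pre-university, and an assumed 10-point excess would appear as about 0.8 to 5 points if a 12-month measure were used. Over the same range, the overall H2 contrast falls only to 8.5 to 9.2 points and H4 to 9.6 to 7.5.

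These sizes depend on the assumed survey month, rates, group shares and progression. The direction, towards no difference, depends on university risk being higher. The primary question on risk factors is not the target of this point. The change is still worth making before baseline, because onset and entry dates are hard to reconstruct afterwards.

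**What to change.** 1. At each survey, record current training level, month of entry to it and approximate onset of any new problem.
2. Treat level as changing over time: assign each new problem to the level held at onset, and end pre-college follow-up at university entry.
3. Answer question 5 and H4 from the follow-ups rather than from Phase 1.
4. For H2 and H3, make the current-problem answer (up to one month) the main level comparison, and report the 12-month NMQ figure descriptively.

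The cost is two or three short items and a few sentences in the protocol. The one-month measure yields fewer events than a 12-month one. It is also only a partial remedy: it still includes problems that began before entry and persist, and in the first weeks of term the one-month window itself reaches back before entry. The onset item is therefore needed for H3.
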